## ADVERSE REACTIONS

**Table 11: Most Common Adverse Reactions (>5.0 Percent) in a Placebo- Controlled Clinical Study of metformin Monotherapy\***

Adverse Reaction	metformin Monotherapy (n=141)	Placebo (n=145)
	% of Patients	
Diarrhea	53.2	11.7
Nausea/Vomiting	25.5	8.3
Flatulence	12.1	5.5
Asthenia	9.2	5.5
Indigestion	7.1	4.1
Abdominal Discomfort	6.4	4.8
Headache	5.7	4.8

\*Reactions that were more common in metformin than placebo treated patients.

In a US double-blind clinical study of metformin in patients with type 2 diabetes, a total of 141 patients received metformin therapy (up to 2550 mg per day) and 145 patients received placebo. Adverse reactions reported in greater than 5% of the metformin patients, and that were more common in metformin- than placebo-treated patients, are listed in Table 1.

Diarrhea led to discontinuation of study medication in 6% of patients treated with metformin. Additionally, the following adverse reactions were reported in □1.0 - □5.0% of metformin patients and were more commonly reported with metformin than placebo: abnormal stools, hypoglycemia, myalgia, lightheaded, dyspnea, nail disorder, rash, sweating increased, taste disorder, chest discomfort, chills, flu syndrome, flushing, palpitation.

## OVERDOSAGE

Overdose of metformin hydrochloride has occurred, including ingestion of amounts greater than 50 grams. Hypoglycemia was reported in approximately 10% of cases, but no causal association with metformin hydrochloride has been established. Lactic acidosis has been reported in approximately 32% of metformin overdose cases. Metformin is dialyzable with a clearance of up to 170 mL/min under good hemodynamic conditions. Therefore, hemodialysis may be useful for removal of accumulated drug from patients in whom metformin overdosage is suspected.

## Appendix 2

### Phone Prescreening Questions to Identify Patients Likely to Be Frail

1. Can you climb two flights of stairs without stopping to rest?
2. Do you have difficulty completing any of the following activities on your own?
  - a. Preparing meals
  - b. Feeding yourself
  - c. Dressing
  - d. Using the toilet
  - e. Housekeeping
  - f. Climbing stairs
  - g. Bathing
  - h. Walking
  - i. Using transportation
  - j. Getting in and out of bed
  - k. Managing medications
3. Which of the following describes your living environment?
  - a. House; apartment; assisted living; nursing home; other
4. Do you depend on any assistive devices such as a cane, wheelchair, braces, walker, or assistance from other people to perform activities important to you in your daily life?
5. Do you wear dentures?
6. Do you have hearing aids?

If the patient answers no to question 1 or yes to any items under question 2, or questions 4-6, then that is a marker of possible frailty. We will invite all patients for the baseline screening visit, if there are 3 or more positive answers that suggest markers of frailty.

### Short Physical Performance Battery

#### 1. Repeated Chair Stands

**Instructions:** Do you think it is safe for you to try and stand up from a chair five times without using your arms? Please stand up straight as quickly as you can five times, without stopping in between. After standing up each time, sit down and then stand up again. Keep your arms folded across your chest. Please watch while I demonstrate. I'll be timing you with a stopwatch. Are you ready? Begin

**Grading:** Begin stop watch when subject begins to stand up. Count aloud each time subject arises. Stop the stopwatch when subject has straightened up completely for the fifth time. Also stop if the subject uses arms, or after 1 minute, if subject has not completed rises, and if concerned about the subject's safety.. Record the number of seconds and the presence of imbalance.. Then complete ordinal scoring.

**Time: \_\_\_\_\_ sec (if five stands are completed)**

**Number of Stands Completed: 1 2 3 4 5**

**Chair Stand Ordinal Score: \_\_\_\_\_**

0 = unable

1 = > 16.7 sec

2 = 16.6-13.7 sec

3 = 13.6-11.2 sec

IRB: 17-003088

Version: 4

Page 17 of 19

4 = < 11.1 sec

## 2. Balance Testing

Begin with a semitandem stand (heel of one foot placed by the big toe of the other foot). Individuals unable to hold this position should try the side-by-side position. Those able to stand in the semitandem position should be tested in the full tandem position. Once you have completed time measures, complete ordinal scoring.

### a. Semitandem Stand

**Instructions:** Now I want you to try to stand with the side of the heel of one foot touching the big toe of the other foot for about 10 seconds. You may put either foot in front, whichever is more comfortable for you. Please watch while I demonstrate.

**Grading:** Stand next to the participant to help him or her into semitandem position. Allow participant to hold onto your arms to get balance. Begin timing when participant has the feet in position and lets go.

#### Circle one number

- 2. Held for 10 sec
- 1. Held for less than 10 sec; number of seconds held \_\_\_\_\_
- 0. Not attempted

### b. Side-by-Side stand

**Instructions:** I want you to try to stand with your feet together, side by side, for about 10 sec. Please watch while I demonstrate. You may use your arms, bend your knees, or move your body to maintain your balance, but try not to move your feet. Try to hold this position until I tell you to stop.

**Grading:** Stand next to the participant to help him or her into the side-by-side position. Allow participant to hold onto your arms to get balance. Begin timing when participant has feet together and let's go.

#### Grading

- 2. Held of 10 sec
- 1. Held for less than 10 sec; number of seconds held \_\_\_\_\_
- 0. Not attempted

### c. Tandem Stand

**Instructions:** Now I want you to try to stand with the heel of one foot in front of and touching the toes of the other foot for 10 sec. You may put either foot in front, whichever is more comfortable for you. Please watch while I demonstrate.

**Grading:** Stand next to the participant to help him or her into the side-by-side position. Allow participant to hold onto your arms to get balance. Begin timing when participant has feet together and let's go.

#### Grading

2. Held of 10 sec
1. Held for less than 10 sec; number of seconds held\_\_\_\_\_
0. Not attempted

**Balance Ordinal Score:** \_\_\_\_\_

0 = side by side 0-9 sec or unable

1 = side by side 10, <10 sec semitandem 2 = semitandem 10 sec, tandem 0-2 sec

3 = semitandem 10 sec, tandem 3-9 sec

4 = tandem 10 sec

### **3. 8' Walk (2.44 meters)**

**Instructions:** This is our walking course. If you use a cane or other walking aid when walking outside your home, please use it for this test. I want you to walk at your usual pace to the other end of this course (a distance of 8'). Walk all the way past the other end of the tape before you stop. I will walk with you. Are you ready?

**Grading:** Press the start button to start the stopwatch as the participant begins walking. Measure the time take to walk 8'. Then complete ordinal scoring.

**Time:** \_\_\_\_\_ sec

**Gait Ordinal Score:** \_\_\_\_\_

0 = could not do

1 = >5.7 sec (<0.43 m/sec)

2 = 4.1-6.5 sec (0.44-0.60 m/sec)

3 = 3.2-4.0 (0.61-0.77 m/sec)

4 = <3.1 sec (>0.78 m/sec)

**Summary Ordinal Score:** \_\_\_\_\_

**Range:** 0 (worst performance) to 12 (best performance). Shown to have predictive validity showing a gradient of risk for mortality, nursing home admission, and disability.

*Reprinted from Guralnik JM, Simonsick EM, Ferrucci L, Glynn RJ, Berkman LF, Blazer DG, Scherr PA, Wallace RB. A short physical performance battery assessing lower extremity function: association with self-reported disability and prediction of mortality and nursing home admission. J Gerontol Med Sci 1994; 49(2):M85-M94*

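### The SPPB form in Appendix 2 gives 8-foot walk times of 5.8 to 6.5 s two different scores, and its tandem-stand assessor text is the side-by-side text

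*Protocol*

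**What the plan says.** The Inclusion Criteria require frailty as determined by the SPPB. The section Measurement of frailty refers to Appendix 2 for the form and repeats the SPPB, with grip strength, at baseline, 3 months and the end of the study.

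Appendix 2, part 3 (8' Walk, 2.44 m), has the rater record seconds and then assign a gait score:

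- "1 = >5.7 sec (<0.43 m/sec)"
- "2 = 4.1-6.5 sec (0.44-0.60 m/sec)"
- "3 = 3.2-4.0 (0.61-0.77 m/sec)"
- "4 = <3.1 sec (>0.78 m/sec)"

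In part 2 (Balance Testing), item c, the participant is asked to stand with "the heel of one foot in front of and touching the toes of the other foot for 10 sec". The assessor's Grading text for that item says "Stand next to the participant to help him or her into the side-by-side position", and starts the clock as in item b: "Begin timing when participant has feet together and let's go". The Balance Ordinal Score key then uses tandem seconds, for example "3 = semitandem 10 sec, tandem 3-9 sec".

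**The concern.** The time bands for gait scores 1 and 2 overlap, and seconds are what the form records. A rater who reads the time column can give either score to the same walk, and the form does not say whether time or speed governs.

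The tandem item gives the participant one stance and the assessor another. An assessor who followed the written text would time an easier stance, or start the clock at the wrong moment, for the hold that separates balance scores 2, 3 and 4.

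Both faults bear on whether a person counts as frail at entry and on change in frailty afterwards. The trial has 12 participants, and the statistical section says its measures of variation will be used to power future studies, so avoidable scoring error would carry into that use.

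**Working it through.** **Inputs.** Distance 2.44 m and the four time and speed bands, all from Appendix 2, part 3. Formula: speed = 2.44 / time.

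**Printed limits against printed speeds.**

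| Time (s) | 2.44 / time (m/s) | Printed speed limit | Agrees? |
|---|---|---|---|
| 3.1 (score 4) | 0.787 | >0.78 | yes |
| 3.2 (score 3) | 0.763 | 0.77 | within rounding of the time |
| 4.0 (score 3) | 0.610 | 0.61 | yes |
| 4.1 (score 2) | 0.595 | 0.60 | yes |
| 6.5 (score 2) | 0.375 | 0.44 | **no** |
| 5.7 (score 1) | 0.428 | 0.43 | yes |

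The 6.5 s limit is the only one that clearly fails. In reverse, 2.44/0.44 = 5.55 s; 5.6 s gives 0.436, which rounds to 0.44.

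**Readings with two scores.** Score 2 as printed covers 25 readings at 0.1 s resolution (4.1 to 6.5 s). With speed rounded to the two decimals printed:

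- 4.1 to 5.6 s (16 readings) gives 0.60 to 0.44, score 2's own speed band.
- 5.7 s (1 reading) gives 0.43, in neither speed band.
- 5.8 to 6.5 s (8 readings) gives 0.42 to 0.38, score 1's speed band.

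Those last eight readings are the ones with two scores by time.

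**Readings with no score by time.** Because the outer bands use strict signs, 3.1 s (gait) and 11.1 s and 16.7 s (chair stands) have no score in the time column. Only one score is plausible for each; for 3.1 s the speed column already gives 4.

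**How often the overlap could occur.** The Protocol gives no gait speeds, so this rests on an assumption: speed normal with mean m and SD s.

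Share in overlap = Φ((0.4281 − m)/s) − Φ((0.3754 − m)/s), where 0.4281 = 2.44/5.7 and 0.3754 = 2.44/6.5.

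| m (m/s) | s (m/s) | Share |
|---|---|---|
| 0.70 | 0.15 | 0.0197 |
| 0.45 | 0.15 | 0.1324 |
| 0.40 | 0.10 | 0.208 |
| 0.80 | 0.15 | 0.0043 |

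The first two rows are the minimum and maximum over m = 0.45 to 0.70 and s = 0.15 to 0.20; the last two lie outside that range.

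The number of assessments depends on whether screening and baseline are one test, as Recruitment of subjects suggests (12 × 3 = 36), or two, as in Measurement of frailty and the Schedule of Events (12 × 4 = 48):

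- 36 × 0.0197 = 0.7 to 36 × 0.1324 = 4.8 walks.
- 48 × 0.0197 = 0.9 to 48 × 0.1324 = 6.4 walks.

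**Tandem text.** The Grading sentences of item b (side-by-side) and item c (tandem) are the same word for word. In the key, with semitandem held for 10 s, 0–2 s of tandem scores 2, 3–9 s scores 3, and 10 s scores 4. No arithmetic can size this fault.

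**The case against.** The strongest reply is that the form largely corrects itself. The speed bands do not overlap and place 5.8 to 6.5 s only in score 1. For the tandem stand, the opening of Balance Testing, the item heading, the participant instruction, the rater's demonstration and the scoring key all point to heel-to-toe, so a trained rater would probably do the right test. Frailty is measured by a second coordinator unaware of treatment, so mis-scoring should not favour an arm. Walk seconds are recorded, so gait can be re-scored. The trial is a pilot without a powered comparison, the form is marked as a reprint, and the frequency range is assumed.

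Much of this stands, and it limits the weight of the point. The frequency range is not a bound; it is the share of walks with two printed scores, not the share mis-scored, and it leaves out people who were screened and not enrolled. The sorting of 5.6 and 5.7 s depends on rounding: unrounded, 5.6 s (0.436) is just below 0.44 and 5.7 s (0.428) is below 0.43. The gaps at 3.1, 11.1 and 16.7 s are minor.

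It does not remove the faults. Nothing tells the rater that speed overrides time, blinding does not protect the eligibility score, and a tandem hold timed from the wrong stance could not be re-scored later. A reprint still governs what the rater does.

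**Conclusion.** Both faults hold and should be fixed. The upper time limit of gait score 2 contradicts its own printed speed, leaving eight readings (5.8 to 6.5 s) with two scores, 1 point of 12 apart. The tandem assessor text describes the wrong stance for a hold that decides balance scores 2 to 4. The gait finding rests only on the 2.44 m distance and the printed bands.

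The frequency of about 2% to 13% of walks (roughly 1 to 5 of 36, or 1 to 6 of 48) rests on the assumed normal distributions; other plausible values give 0.4% or 21%. The effect on eligibility cannot be stated without an SPPB cut-off, and the effect of the tandem text cannot be estimated. Neither fault invalidates the trial.

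**What to change.** On the Appendix 2 form:

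1. End gait score 2 at 5.6 s and write score 1 as ≥5.7 s, after confirming both against the published battery that the form cites. The page alone does not settle 5.7 s.
2. Replace the tandem assessor text with: help the participant into the heel-to-toe (full tandem) position, and begin timing when the feet are heel-to-toe and the participant lets go.
3. In the same edit and source check, close the small gaps: gait score 4 as ≤3.1 s, chair score 4 as ≤11.1 s, chair score 1 as ≥16.7 s, with walk and chair times recorded to 0.1 s. Every reading then has exactly one score.
4. Derive gait and chair scores from the recorded seconds, and re-score tests already done.

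The cost is one appendix page and one look at the source. Re-scoring walks and chair stands needs no new data, because the form already records their times. Any tandem hold timed with feet together is not recoverable, which is a reason to correct the form promptly.
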